**ABSTRACT**

Approximately 66% of those diagnosed with colorectal cancer who will survive for at least 5 years post diagnosis need to take a more active role in their care to optimize their health outcomes. Standard care includes providing survivorship care plans that initially focused on information delivery alone, which has demonstrated limited efficacy for improving health outcomes. An increased emphasis on the process of patient engagement and support of non-pharmacologic self-management (SM; symptom management, medication adherence, screening, healthy behaviors) is needed to improve care plans. Holistic consideration of individual-level contextual factors such as values or tradeoffs with existing behaviors, could more sustainably integrate SM into survivors' life context. Facilitating SM with consideration of context is consistent with systems thinking. System Support Mapping (MAP) is a systems thinking activity that involves creating a visual diagram of how SM occurs within cancer survivors' life context that facilitates self-awareness and patient-driven engagement in SM. We propose to conduct a one-arm pilot study of MAP among 24 colorectal cancer survivors within one year of completing active treatment to describe study feasibility, intervention acceptability, and outcome variability. MAP can also be a powerful tool to reduce health disparities since it allows for simultaneous consideration of individual-level and multi-level contextual factors (i.e., geographic, social, institutional). Health disparities exist such that colorectal cancer survivors who are rural residents have higher cancer mortality than do urban cancer survivors. Furthermore, rural survivors are at increased risk for self-reported poorer health and engage in more health compromising behaviors compared to urban survivors. Therefore, we will also identify multi-level contextual factors influencing SM and examine how study results vary by rural-urban context to inform future studies. MAP is a novel approach that may generalize to improving care for other chronic illnesses such as cardiovascular disease.

## Use of Systems Support Mapping to Guide Patient-Driven Self-Management in Rural and Urban Cancer Survivors

Wake Forest Baptist Comprehensive Cancer Center (WFBCCC)  
WFBCCC # 99118

### 1.0 Introduction and Background

Cancer survivors need to engage in self-management (SM) to improve health outcomes. Approximately 66% of the 135,000 people diagnosed with colorectal cancer in the United States each year will survive for at least 5 years post diagnosis. As cancer survivors are expected to live longer, there is a shift in perspective to viewing cancer as a chronic illness, which is accompanied by increased need for cancer survivors to partner with physicians and become more actively engaged in SM to optimize their own health outcomes. The Institute of Medicine and others recommend that patients receive a comprehensive survivorship care plan when transitioning from active treatment to survivorship that provides a treatment summary and outlines follow-up care needs including multiple complex SM activities (e.g., psychosocial support, symptom management, health behaviors). A weakness of initial research on survivorship care plans is that interventions have solely focused on information delivery and demonstrated limited efficacy for improving self-reported health outcomes. Recommended future directions for improving upon information-focused survivorship care planning involve increasing the emphasis on the process of patient engagement and support of non-pharmacologic SM (e.g., health behaviors). One particularly *strong* survivorship care planning intervention that improved self-reported health was designed to be patient-centered and focused on the process of engaging cancer survivors with one session that included goal setting, establishing a plan to improve health, and increasing the motivation, information, skills, and confidence necessary to engage in SM. Yet, this intervention focused on survivors' cancer treatment narrative and did not holistically consider individual-level contextual factors such as values or tradeoffs with existing behaviors, which would more sustainably integrate SM into survivors' existing life context and ultimately facilitate translation of the intervention into practice.

Self-awareness of contextual influences on behavior will engage survivors in sustainable SM. The conceptual framework for improving the quality of cancer care presented in an Institute of Medicine report starts with engaged patients. This report defines patient engagement in cancer care as "A system that supports all patients in making informed medical decisions consistent with their needs, values, and preferences in consultation with their clinicians who have expertise in patient-centered communication and shared decision making." Self-determination Theory also emphasizes that supporting patients' partnership in healthcare decisions will enhance patients' engagement in SM and ultimately lead to more sustainable improvement in health outcomes. According to Self-determination Theory, self-awareness is a necessary first step in facilitating patients' patient-driven (i.e., autonomous) motivation for engaging in SM. Patient-driven goals are more likely to be achieved than goals that are extrinsically motivated. This point is illustrated by an intervention to facilitate the SM in other chronic diseases that provided participants with the opportunity to self-select their goals rather than prescribing specific behavior changes. Results showed that this process of patient-driven goal setting successfully changed health behaviors and reduced hospitalizations. Yet, patients may need guidance to facilitate self-awareness and identify what they need to engage in multiple recommended SM activities with consideration of their broader life context.

[figure not shown]
Systems Support Mapping (MAP) facilitates self-awareness of contextual factors. Systems thinking unpacks complex behaviors (e.g., SM), while exploring how individual patient choices are facilitated and constrained by broader contextual systems. System Support Mapping (MAP) is a structured systems thinking activity to facilitate survivors' creation of a visual diagram to tangibly illustrate and create self-awareness for how a SM behavior relates to the broader context of tradeoffs with other behaviors and achieving most-valued outcomes. MAP facilitates self-awareness of the complex broader system and the ability for patients to clearly identify any discrepancies or intervention targets for SM. Highlighting discrepancies between current and desired states is used as a technique to generate patient-driven motivation for behavior change. Tying individual SM behaviors to broader life values

## Use of Systems Support Mapping to Guide Patient-Driven Self-Management in Rural and Urban Cancer Survivors

Wake Forest Baptist Comprehensive Cancer Center (WFBCCC)  
WFBCCC # 99118

may also increase the perceived importance of SM goals and thus patient engagement. Similarly, identifying how changing SM holistically affects broader contextual systems will more sustainably integrate SM. Having patients select patient-driven goals for SM with a consideration of their life context will set the stage for engaging in patient-driven SM. MAP has primarily been applied to systems in the community setting with the exception of [name] (Co-Investigator) work in collaboration with [name] (Consultant) that took an individual-focused approach to understanding SM and health equity in women with migraine occupying lower social locations. Thus, it is novel to apply an individual-focused MAP to guide patient engagement in SM with a focus on non-pharmacologic approaches during the transition from active cancer treatment to survivorship.

MAP can be a powerful tool to reduce health disparities since it allows for simultaneous consideration of (1) individual-level and (2) multi-level contextual factors. Rural cancer survivors' are especially likely to benefit from guidance to facilitate self-awareness and select patient-driven goals due to their need to consider complex multi-level contextual factors (i.e., geographic, social, institutional). For example, geographic context is associated with the ability to access to supportive care services (e.g., psychologist, religious leader). Rural residents may share a social context such as the importance of self-reliance. Furthermore, results from our research and others show that a large portion (30-40%) of cancer survivors seek methods for SM outside of conventional cancer care institutions through means such as use of complementary health approaches (CHA) at higher rates than the general public and use of CHA is higher in rural communities. Thus, interventions are needed that consider multi-level contextual factors in order to optimize SM and address rural-urban disparities in health outcomes. Health disparities exist such that colorectal cancer survivors who are rural residents have higher cancer mortality than do urban cancer survivors. Furthermore, rural survivors are generally at increased risk for self-reported poorer health (e.g., psychological distress, symptoms) and engage in more health compromising behaviors (e.g., smoking and physical inactivity) compared to urban survivors. Such health compromising behaviors are associated with mortality. MAP may improve individual-level SM, while also identifying how individual-level SM interacts with multi-level contextual factors associated with rural-urban disparities (e.g., education, travel barriers). Additionally, MAP will identify key stakeholders and leverage points needed to inform future multi-level studies. Figure 1 shows the proposed conceptual model, which places Self-Determination Theory in context of other factors influencing patient-centered care and health disparities.

# Use of Systems Support Mapping to Guide Patient-Driven Self-Management in Rural and Urban Cancer Survivors

Wake Forest Baptist Comprehensive Cancer Center (WFBCCC)  
WFBCCC # 99118

## 2.0 Objectives

We will conduct a one-arm pilot study of MAP among 24 colorectal cancer survivors within one year of completing active treatment. We will quantitatively and qualitatively describe recruitment and retention; intervention completion and acceptability; and variability and changes in proposed outcomes (i.e., measures of patient engagement, health outcomes) to guide future study planning. We will analyze collected maps, and describe factors and targets for intervention at multiple levels (individual/geographic/social/institutional).

### 2.1 Primary Objective

2.1.1 To evaluate the feasibility of the MAP intervention in colorectal cancer survivors, as characterized by enrollment, intervention adherence, and retention rates.

*We hypothesize >50% of eligible patients will enroll and that >70% of participants will complete the intervention and be retained in the study.*

### 2.2 Secondary Objectives

2.2.1 To evaluate intervention acceptability as characterized by participant ratings.

2.2.2 To describe outcome variability to inform future studies.

2.2.3 To identify multi-level contextual factors influencing SM.

2.2.4 To qualitatively assess feasibility, acceptability using semi-structured interviews.

2.2.5 To examine how study results vary by rural-urban context.

## 3.0 Patient Selection

We will enroll 24 participants with equal numbers of patients from urban and rural communities over 10 months. To identify potential patients, programming with Epic will be used to provide automated reports identifying patients within one year of completing active treatment for colorectal cancer. We will also post the study on Be Involved. The Project Manager will screen the report and communicate with attending physicians, physician assistants, clinic nurses and/or the patient navigator regarding patients' potential eligibility for the study. Research staff will approach patients either in person or remotely (e.g., telephone, myWakeHealth, mail) regarding their interest in study participation. Ways to contact the study team if they wish to opt out of the study will be included. A study team member will then follow up with all patients who respond to the letter with an interest in participation. Of the patients who do not decline, the study coordinator will approach at their next clinic visit or by phone to provide study information and answer questions to determine willingness to participate. The consent will be signed remotely or in person. If signed remotely, patients will be asked to send the form back to us by a secure means (e.g., REDCap, mail). In the case that the patient is consented remotely, either a hard copy or email attachment of the informed consent document will be provided to the participant. We will compensate participants \$50.

We will document recruitment in a Screening Log including reasons for ineligibility, eligible patients approached, number who declined participation, and number successfully recruited. After making sure

## **Use of Systems Support Mapping to Guide Patient-Driven Self-Management in Rural and Urban Cancer Survivors**

Wake Forest Baptist Comprehensive Cancer Center (WFBCCC)  
WFBCCC # 99118

the patient clearly understands the study procedures and agrees to follow them, the patient will be asked to sign the informed consent form. A copy of the consent form will be given to the participant, and the original copy will be kept in the participant's file.

### **3.1 Inclusion Criteria**

- 3.1.1** Adults  $\geq 18$  years of age
- 3.1.2** Diagnosed with stage I-III colorectal cancer
- 3.1.3** Within 2 years of completing active treatment for colorectal cancer
- 3.1.4** Cognitively able to complete interviews as judged by the study team
- 3.1.5** Able to understand, read and write English

Children under the age of 18 with colorectal cancer will be excluded due to the rarity of colorectal cancer in this population according to the National Cancer Institute (incidence rate  $\leq 0.6$ ) and because they are likely to have distinct needs and experiences if diagnosed this young. Further, it is unlikely that the study would recruit sufficient numbers in this subset of the cancer survivor population to gain meaningful results. Results from this research may inform future studies in children with cancer under 18 who are generally different from adults and should be researched separately.

### **3.2 Exclusion Criteria**

- 3.2.1** Declined participation in the study

### **3.3 Inclusion of Women and Minorities**

The target population for this study is adult men and women who have completed active treatment for colorectal cancer. We expect that women and minorities will be represented as is consistent with the proportion seen in the past five years at the Wake Forest Baptist Comprehensive Cancer Center. For this pilot study, non-English speaking patients will be excluded because the intervention will be implemented in English. Pending results of the pilot, a future study to determine the efficacy of translating the intervention will be proposed. Experts at Wake Forest Baptist Comprehensive Cancer Center's Office for Cancer Health Equity will review our protocol and suggest additional strategies to enhance the ability to recruit a representative sample. The OCHE includes a Hispanic Clinical Trial Patient Navigator who provides guidance to Hispanic participants throughout the research process and will be involved in educating any potential Hispanic study participants on clinical trials prior to in-person interaction with the Project Manager. The intervention is designed to reduce barriers to recruitment and to be presented in a manner that will be culturally sensitive with the aim of reaching all patients.

## **4.0 Registration Procedures**

All patients entered on any WFBCCC trial, whether treatment, companion, or cancer control trial, must be linked to the study in EPIC within 24 hours of Informed Consent. Patients must be registered prior to the initiation of treatment.

## Use of Systems Support Mapping to Guide Patient-Driven Self-Management in Rural and Urban Cancer Survivors

Wake Forest Baptist Comprehensive Cancer Center (WFBCCC)  
WFBCCC # 99118

You must perform the following steps in order to ensure prompt registration of your patient:

1. Complete the Eligibility Checklist (Appendix A)
2. Complete the Protocol Registration Form (Appendix B)
3. Alert the Cancer Center registrar by phone, *and then* send the signed Informed Consent Form, Eligibility Checklist and Protocol Registration Form to the registrar, either by fax or e-mail.

\*Protocol Registration is open from 8:30 AM - 4:00 PM, Monday-Friday.

4. Fax/e-mail ALL eligibility source documents with registration. Patients will not be registered without all required supporting documents.

Note: If labs were performed at an outside institution, provide a printout of the results. Ensure that the most recent lab values are sent.

To complete the registration process, the Registrar will:

- assign a patient study number
- register the patient on the study

## 5.0 Study Outcomes and Study Measures

We will collect data at two different levels, the individual-level (feasibility, outcome measures), and multi-level contextual factors (MAP data). We will collect self-reported data either remotely or in person at baseline and two weeks after MAP.

### 5.1 Primary Outcome (Feasibility)

Enrollment rate will be calculated as the percent of eligible participants approached who agree to participate.

Participation rate will be calculated as the percent of participants who complete the study intervention among those enrolled.

Retention rate will be calculated as the number of participants who complete the study measures among those enrolled.

### 5.2 Secondary Outcomes

#### 5.2.1 Self-reported ratings of intervention acceptability

#### 5.2.2 Proximal outcomes

- 5.2.2.1 Measures of autonomy [Index of Autonomous Functioning]
- 5.2.2.2 Self-efficacy for managing cancer [Self-efficacy to Manage Chronic Disease Scale and PROMIS self-efficacy for managing symptoms short form]
- 5.2.2.3 Relatedness [HEAL Patient-Provider Connection], only assessed at follow-up because this construct is assessing the experience with the MAP facilitator.

## Use of Systems Support Mapping to Guide Patient-Driven Self-Management in Rural and Urban Cancer Survivors

Wake Forest Baptist Comprehensive Cancer Center (WFBCCC)  
WFBCCC # 99118

### 5.2.3 Health outcomes

- 5.2.3.1 Psychological stress [Perceived Stress Scale, 4-item]
- 5.2.3.2 Symptoms [PROMIS Profile 29]
- 5.2.3.3 Health behaviors [items on tobacco use, physical activity, use of CHA]

### 5.2.4 Qualitative assessment of feasibility, acceptability and changes in outcomes with semi-structured interviews

### 5.2.5 Qualitative analysis of systems support maps

### 5.2.6 Demographic (age, rural-urban residence [classified by the Federal Office of Rural Health Policy definition of rural], race/ethnicity, marital status, education level, health literacy, financial toxicity)

### 5.2.7 Clinical factors (cancer type, disease stage, recurrence status, type of treatment) factors will be abstracted from medical charts or self-reported.

## 6.0 Study-Related Activities

### 6.1 Overview of Study-Related Activities

	Pre-Study a	Baseline	MAP b Intervention c	Follow-up (2-week) d
Recruitment	X			
Informed consent	X			
Demographic and Clinical Factors		X		
Patient-Reported Outcomes		X		X
Intervention Completion			X	
Acceptability Ratings				X
Semi-structured Interview				X
Adverse event evaluation			X	X

a Pre-study requirements listed in table must be completed within 30 days prior to registration.

b MAP = Systems Support Mapping

c Intervention may be coordinated with future clinic visit; must be completed within 6 months of registration

d Follow-up visit to be completed 14 - 28 days after intervention

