### 9.3 Power and Sample Size

The target sample size is based on estimating rates of feasibility measures to inform the design of an efficacy trial. If the recruitment rate is below 50% and intervention completion and retention rates are below 70%, a larger study may not be feasible. Assuming a negative binomial distribution and true rate of 50%, the probability that we would have to approach 61 or more people to recruit 24 is <0.05. Therefore, if we approach  $\geq 61$  participants to enroll 24, it is unlikely the true probability is above 50%, and we will conclude the study may not be feasible. Out of the 24 participants, if the true rate of intervention completion and study retention is 70%, we expect 13 or more will participate/be retained, so if 12 or fewer do not participate/are not retained the study may not be feasible; we have 80% power to test that the hypothesis that the rate is 70% compared to the alternative that is 46% or less. The number of participants interviewed will be determined when theoretical saturation is reached. We estimate that we will need 8-12 participants in each group (rural-urban).

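### Enrollees who consent but never have the MAP session are not scheduled to be asked why, so the interviews on feasibility draw only on people for whom MAP was feasible

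*Combined protocol and SAP*

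**What the plan says.** All from the combined protocol and SAP.

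- **Timing of follow-up.** Section 5.0: "We will collect self-reported data either remotely or in person at baseline and two weeks after MAP". Section 6.1, footnote d: "Follow-up visit to be completed 14 - 28 days after intervention". The schedule in 6.1 places follow-up patient-reported outcomes, acceptability ratings and the semi-structured interview at this one visit.
- **Window for MAP.** Section 6.1, footnote c: "Intervention may be coordinated with future clinic visit; must be completed within 6 months of registration".
- **Denominators.** Section 5.1: "Participation rate will be calculated as the percent of participants who complete the study intervention among those enrolled", and "Retention rate will be calculated as the number of participants who complete the study measures among those enrolled". Section 6.5 adds no removal criteria, so someone who misses MAP stays enrolled and is counted.
- **Targets.** Section 2.1: "We hypothesize >50% of eligible patients will enroll and that >70% of participants will complete the intervention and be retained in the study". Section 9.3 applies one 70% benchmark and one cut, 13 or more of 24, to both completion and retention.
- **Use of the interviews.** Objective 2.2.4: "To qualitatively assess feasibility, acceptability using semi-structured interviews".
- **People who decline.** Section 3.0 has a Screening Log and section 8.0 lists Decline Forms. Section 8.0 also lists an Intervention Completion Form, whose content is not reproduced.

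**The concern.** A feasibility pilot needs to learn why people who agreed to take part did not get as far as the intervention. This plan has instruments for those who decline and for those who attend. The group in between, who consent and then do not have MAP, has baseline data and a place in both denominators but no scheduled contact afterwards.

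MAP may be up to 6 months after registration and may be tied to a clinic visit, so this group could well not be empty. Their reasons are direct evidence on feasibility. They may also bear on objective 2.2.5, since section 1.0 names travel among the barriers that may differ between rural and urban survivors. As scheduled, the qualitative assessment of feasibility hears only from people for whom the session proved feasible.

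A second, smaller matter is that section 9.3 treats completion and retention as parallel measures and does not say that, on this schedule, one is contained in the other.

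**Working it through.** **1. The plan's own figures.** N is 24. For enrollment, section 9.3 states that "the probability that we would have to approach 61 or more people to recruit 24 is <0.05" at a true rate of 50%. Needing 61 or more approaches means at most 23 enrolled among the first 60: P(X ≤ 23 | 60, 0.50) = 0.046, which agrees. For completion and retention, P(X ≤ 12 | 24, 0.70) = 0.031. (The sentence in 9.3 is worded as 12 or fewer *not* retained; I read it as 12 or fewer retained, which is what fits the 13-or-more cut.) Nothing below changes N or these cuts.

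**2. Who is missed.** Let c be the proportion of enrollees who have MAP. The documents give a target for c but no expected value, so the range is an assumption. Enrollees with no scheduled interview = 24 × (1 − c):

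- c = 0.70: 24 × 0.30 = 7.2, about 7
- c = 0.85: 24 × 0.15 = 3.6, about 4

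**3. Nesting.** Let q be the proportion of MAP completers who complete follow-up (not given; assumed). As scheduled, nobody without MAP reaches follow-up, so retention = c × q ≤ c. The chance of 12 or fewer of 24 retained:

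| c | q | c × q | P(12 or fewer) |
|---|---|---|---|
| 0.70 | 1.00 | 0.700 | 0.031 |
| 0.70 | 0.95 | 0.665 | 0.070 |
| 0.70 | 0.90 | 0.630 | 0.135 |
| 0.70 | 0.85 | 0.595 | 0.228 |
| 0.80 | 0.90 | 0.720 | 0.018 |
| 0.85 | 0.85 | 0.7225 | 0.017 |

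With completion exactly at the boundary, any loss after MAP raises the chance of failing the rule. With completion moderately above it, the chance is below the 0.031 in step 1.

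**4. Whether the two losses can be told apart.** Completed/24 and retained/24 are both planned (5.1, 9.1.1). If 17 complete and 14 are retained, 24 − 17 = 7 never had MAP and 17 − 14 = 3 were lost afterwards. No further data are needed.

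**5. What would happen if non-completers could count as retained.** Suppose a proportion q2 of them returned a shortened questionnaire that counted. Retention would be c × q + (1 − c) × q2. With c = 0.70, q = 0.90, q2 = 0.50: 0.63 + 0.15 = 0.78, and P(12 or fewer) falls from 0.135 to 0.002, with no more sessions delivered. The retention definition should therefore stay as it is.

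**The case against.** The strongest reply is that the primary analysis is sound as written. All enrolled is a conservative denominator, the hypothesis in 2.1 can be read as requiring completion and retention jointly, and a pilot may legitimately demand both. All of that stands.

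A reader might go further than the documents allow in four ways:

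- **That the retention result cannot show where people are lost.** It can: step 4 shows the subtraction, because the two rates share a denominator.
- **That the rise from 0.031 to 0.228 measures the harm of timing follow-up from MAP.** It needs completion exactly at 70% and an assumed 85% follow-up, and it reflects loss among attenders. At 80% × 90% or 85% × 85% the figure is 0.018 or 0.017.
- **That the interview numbers are at risk.** With 12 per group and 70% available, the chance that both groups reach 8 is 0.724² = 0.52; at 85% it is 0.976² = 0.95. Section 9.3 lets saturation decide the number and gives 8–12 only as an estimate. Interviews on why MAP was missed would not clearly add to saturation on the MAP experience.
- **That the acceptability ratings are biased upward.** The mapping-satisfaction and HEAL items, and most of the future-planning items, presuppose the session. Only one general item and three facility ratings could be put to non-attenders, and the documents give no evidence of the direction of any bias.

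It is also fair to say that the gap is inferred from silence. Nothing forbids contacting a non-attender, 5.1 ties the study measures to no time point, and the Intervention Completion Form may record a reason. But no visit, window or instrument is defined for these people, and a reason on a form is not the interview that 2.2.4 relies on.

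**Conclusion.** The point holds as a cheap improvement to what the pilot learns; it is not a flaw in the primary analysis. As scheduled, consented people who never have MAP have no route into the qualitative feasibility assessment. That is about 7 of 24 if completion is 70% and about 4 if it is 85%; both rates are assumptions, and the number would be nil if everyone attended. Enrollment and completion rates still count everyone, and N, the 61-approach cut and the 12-or-fewer rule are untouched. Retention is nested in completion on this schedule. That is a legitimate choice which section 9.3 should state, so that the two results are not read as independent.

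**What to change.** 1. In section 6.1, footnote d, and section 5.0, add that an enrollee who withdraws from MAP, or reaches the end of the 6-month window without it, is offered the semi-structured interview remotely, on the reasons for not completing. Analyse these interviews as a separate group under 2.2.4.
2. Leave retention among all enrolled as defined in 5.1, and say that non-completers count as not retained for the 9.3 rule, whether or not they give an interview.
3. State in 9.2 that no data from non-completers enter the change and variance estimates.
4. Add a sentence to 9.3 that retention is nested in completion as scheduled, and that losses before and after MAP are read from the two planned rates.

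The cost is a short amendment and, over the assumed range, some 4 to 7 extra remote contacts with people who have already consented. Section 5.0 already allows remote collection of self-reported data. Some of those contacted will not respond, so the information will be partial.
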